7.3 End of Treatment/Withdrawal

Subjects shall discontinue study treatment upon the occurrence of an event that meets the "5.3.1 Criteria for subject withdrawal/treatment discontinuation". At the end of the study treatment or upon withdrawal from the study, if a subject has not undergone examinations within 14 days prior to the end of the study, the subject should undergo the following examinations:

[Hematology] [Blood biochemistry] [Urinalysis] [Routine stool test] [Coagulation function] [Pregnancy test] [Thyroid function test] [Myocardial zymogram] [Vital signs] [Physical examinations and weight measurement] [ECOG PS] [ECG] [Echocardiogram] [Blood pressure monitoring] [Adverse events] [Concomitant medication] [Return of apatinib]

If a subject has not undergone imaging examinations within 4 weeks prior to the end of the study, the subject should undergo an imaging examination at the end of the study treatment or upon withdrawal from the study. For subjects with PD demonstrated by non-imaging evidence (intolerability, other conditions), a tumor evaluation will be carried out every 3 months until PD, death, or the initiation of other tumor treatments.

7.4 Follow-up Period

30 days after discontinuation/end of treatment

[Vital signs] [Physical examinations and weight measurement] [ECOG PS] [Hematology] [Urinalysis] [Blood biochemistry] [Adverse events] [Concomitant medication]

Adverse events will be recorded from the time when the subjects sign the informed consent form. AEs unrelated to the study drugs will be recorded to 30 days after the last dose.

Treatment-related AEs will be collected until 90 days after the last dose of SHR-1210 or 30 days after the last dose of targeted anti-angiogenic therapy (whichever is longer). See the AE/SAE collection time limit in Section 8.3 for details.

[Survival follow-up] After the study treatment is discontinued, the survival status and subsequent anti-tumor treatment can be collected through clinical or telephone follow-ups every 2 months until death.

Schedule of Activities

Item	Screening Period			Treatment Period (28 days/cycle)			Post-Treatment		Survival Follow-up
	Within 3 weeks before administration	Within 1 week before administration	Cycle 1		Cycles 2-26		End of Treatment/ Withdrawal (+ 3 d)	End of treatment visit (± 3 d)	Every 2 months (±3)
			Day 1	Day 15 (± 3 d)	Day 1 (± 3 d)	Day 15 (± 3 d)			
Baseline Data									
Signing of Informed Consent	×								
Demographics	×								
Tumor History/ Other Medical History ^[1]	×								
Concomitant Medication ^[2]		×	×	×					
Laboratory Tests									
Hematology ^[3]		×		×	×	×	×	×	
Urinalysis ^[4]		×		×	×	×	×	×	
Routine Stool Test ^[5]		×		×	×		×		
Blood biochemistry ^[6]		×		×	×	×	×	×	
Coagulation Function Test ^[7]		×		×	×		×		
T3, FT3, FT4, and TSH ^[8]	×				×		×		
Pituitary Adrenal Axis Test ^[9]	×								

Item	Screening Period			Treatment Period (28 days/cycle)			Post-Treatment		Survival Follow-up
	Within 3 weeks before administration	Within 1 week before administration	Cycle 1		Cycles 2-26		End of Treatment/ Withdrawal (+ 3 d)	End of treatment visit (± 3 d)	Every 2 months (±3)
			Day 1	Day 15 (± 3 d)	Day 1 (± 3 d)	Day 15 (± 3 d)			
Myocardial Zymogram ^[10]		×					×		
HBV, HCV, and HIV Tests ^[11]	×								
Pregnancy Test ^[12]		×					×		
Detection of EGFR Mutations and ALK Fusion Genes ^[13]	×								
Clinical Evaluation and Examination									
Adverse Events ^[14]	From informed consent to 30 days after the last dose								
Vital Signs ^[15]		×	×	×	×	×	×	×	
Physical Examination and Weight Measurement ^[16]		×	×	×	×	×	×	×	
ECOG PS		×			×		×	×	
ECG ^[17]		×		×	×	×	×		
Echocardiography ^[18]		×					×		
Blood Pressure Monitoring ^[19]				×	×	×	×		
Pulmonary Function Test ^[20]	×								

Item	Screening Period			Treatment Period (28 days/cycle)			Post-Treatment		Survival Follow-up
	Within 3 weeks before administration	Within 1 week before administration	Cycle 1		Cycles 2-26		End of Treatment/ Withdrawal (+ 3 d)	End of treatment visit (± 3 d)	Every 2 months (±3)
			Day 1	Day 15 (± 3 d)	Day 1 (± 3 d)	Day 15 (± 3 d)			
STUDY DRUGS									
Administration of SHR-1210 ^[21]			×	×	×	×			
Administration of Apatinib ^[22]			Oral administration once a day after meal						
Dispensation/Return of Apatinib ^[23]		×	×	×	×	×	×		
Imaging Evaluation									
Imaging Examination ^[24]	×		Once every 2 cycles in the first 6 cycles, followed by once every 3 cycles				×		
Follow-Up After End of Treatment									
Time to Progression ^[25]							Imaging evaluation will be carried out once every 3 months (± 7 d) until progressive disease or the initiation of other cancer treatments (subjects with non-imaging PD)		
Time of Death ^[26]									×
Blood Sampling and Tumor Tissue Sampling/Sample Collection									
PK Blood Sampling ^[27]			×	×	×	×			
Collection and Detection of Biomarkers ^[28]	×								

Note:

- [1] History of tumor/other diseases: reports of pathological findings, detection of EGFR mutations, and detection of ALK fusion gene; history of tumor surgery, chemotherapy, radiotherapy, and other disease treatments; history of tumor other than non-small cell lung cancer.
- [2] Record the concomitant medication and concomitant treatment given within 30 days prior to randomization and during the study period. Once the study treatment is interrupted, only the concomitant medication and treatment used to solve new or unresolved treatment-related AEs will be recorded.
- [3] Hematology: Hemoglobin, red blood cell count, white blood cell count, neutrophil count, lymphocyte count, and platelet count will be measured within 7 days before enrollment, on Day 15 of Cycle 1, Day 1 and Day 15 of subsequent cycles, upon completion of the study, and 30 days after the end of treatment.
- [4] Urinalysis: Urine protein, urine glucose, and urine occult blood (urine red blood cells and white blood cells). If two consecutive semi-quantitative protein tests show urine protein 2-3+, then a quantitative 24-h urine protein test is required. If semi-quantitative protein test shows urine protein > 3+, then a quantitative 24-h urine protein test shall be performed. The tests will be carried out within 7 days before the enrollment, on Day 15 of Cycle 1, Day 1 and Day 15 of subsequent cycles, upon completion of the study, and 30 days after the end of treatment.
- [5] Routine stool test: Occult blood; re-examination is required for fecal occult blood+; if fecal occult blood is confirmed, then a gastroscopy shall be performed. The test will be performed within 7 days before enrollment, on Day 15 of Cycle 1 and Day 1 of subsequent cycles, and upon completion of the study.
- [6] Blood biochemistry: bilirubin total, bilirubin conjugated, ALT, AST, AKP, γ -GT, protein total, albumin, urea or urea nitrogen, creatinine, uric acid, fasting blood glucose, TG, cholesterol, potassium, sodium, chlorine, calcium, phosphorus, blood lipase (only during the screening period and in the case of subsequent abdominal pain, abdominal distension and other symptoms of suspected pancreatitis), blood amylase (only during the screening period and subsequent abdominal pain, abdominal distension, and other symptoms of suspected pancreatitis). It will be carried out within 7 days before enrollment, on Day 15 of Cycle 1, Day 1 and Day 15 of subsequent cycles, upon completion of the study, and 30 days after the end of treatment.
- [7] Coagulation function: INR, APTT, PT, TT, FIB. The test will be performed within 7 days before enrollment, on Day 15 of Cycle 1 and Day 1 of subsequent cycles, and upon completion of the study.
- [8] Thyroid function test: including serum FT3, FT4 and TSH. The test will be performed 21 days before administration, on Day 1 of Cycle 2, and then once every 3 cycles.
- [9] Examination of the pituitary adrenal axis: including the tests of ACTH, cortisol, and sex hormones; carried out during the screening period.
- [10] Myocardial zymogram: Perform once within 7 days before enrollment and retest only upon the onset of symptoms of precordial pain and palpitations, and abnormal electrocardiograms hereafter; perform upon completion of the study.

- [11] Hepatitis B, hepatitis C, and HIV tests: hepatitis B panel [If the test results are abnormal, viral replication (HBV DNA) test should be performed]; hepatitis C virus antibody (anti-HCV) test (If the test results are abnormal, virus titer should be tested); HIV antibody test.
- [12] Pregnancy test: The urine pregnancy test will be performed 72 h before the first dose for females of a childbearing age. If the result of the urine pregnancy test is positive, a serum pregnancy test shall be performed. If necessary, re-tests can be performed for confirmation.
- [13] If the subjects have previously been tested for EGFR mutations and ALK fusion gene, retests are not required; otherwise, the study site will perform relevant tests. If the subjects are positive for EGFR mutations, the test of ALK fusion gene will no longer be performed.
- [14] Adverse events: Adverse events will be collected from the time when the subjects sign the informed consent form. AEs unrelated to the study drugs will be collected to 30 days after the last dose. Treatment-related AEs will be collected until 90 days after the last dose of SHR-1210 or 30 days after the last dose of targeted anti-angiogenic therapy (whichever is longer). See the AE/SAE collection time limit in Section 8.3 for details.
- [15] Vital sign examination: Body temperature, respiration, pulse, blood pressure. The examination will be performed within 7 days before enrollment, on Day 1 and Day 15 of Cycle 1, Day 1 and Day 15 of subsequent cycles, upon completion of the study, and 30 days after treatment.
- [16] Physical examination and weight measurement: Examination of major body systems (head and face, skin system, lymph nodes, eyes, ears, nose, throat, oral cavity, respiratory system, cardiovascular system, abdomen, urogenital system, musculoskeletal system, nervous system and mental state) will be performed within 7 days before enrollment, on D1 and D15 of Cycle 1, D1 and D15 of subsequent cycles, upon completion of the study, and 30 days after the end of treatment. Body weight measurement will be started on D1 of Cycle 2 and carried out on D1 of subsequent cycles, upon completion of the study, and 30 days after the end of treatment.
- [17] 12-Lead ECG: Performed within 7 days before enrollment, on Day 15 of Cycle 1, Day 1 and Day 15 of subsequent cycles, and upon completion of the study. Abnormalities in ECG must be confirmed twice via additional ECG tests.
- [18] Echocardiography: Performed within 7 days prior to the enrollment and upon completion of the study, and when clinically significant abnormalities are found during the study.
- [19] Blood pressure monitoring: The blood pressure monitoring will be performed by the subjects themselves and recorded in their diary card. Blood pressure will be measured at least 3 times a week in the first 2 cycles. If the blood pressure is abnormal, the measurement will be carried out every day; If the blood pressure is normal, the blood pressure measurement will be carried out twice a week after 2 cycles; In addition, the blood pressure will be measured by the investigator during each follow-up. During each blood pressure measurement, smoking and coffee are prohibited for 30 min before the measurement, and subjects should at least rest for 10 min, and the sitting position will be taken during the measurement by placing the elbow at the same level as the heart. Each blood pressure measurement will be taken on the same side of the body.

- [20] Pulmonary function test: Maximum vital capacity, the forced expiratory flow at 25-75% of forced vital capacity (FEF25-75), the peak expiratory flow rate (PEF), the maximum expiratory volume per second, diffusing capacity of the lungs for carbon monoxide (DLCO) and oxygen saturation. The test will be carried out during the screening period and then according to the judgment of the investigator in subsequent cycles.
- [21] SHR-1210 administration: SHR-1210 will be administered via intravenous injection (no prophylactics) with a fixed dose of 200 mg given in 30 min (no less than 20 min and no more than 60 min), once every 2 weeks. Each cycle contains 4 weeks (the subjects for the expanded PK study receive one dose on D1 of Cycle 1) and the longest period of drug use is 2 years. After 6 cycles of SHR-1210 administration, the treatment can be discontinued if the imaging evaluation confirms a CR.
- [22] Apatinib will be taken orally after meals, once a day, and continued throughout the study (the subjects for the expanded PK study receive the drug starting on Day 22 of Cycle 1. The administration on Day 28 of Cycle 1 and Day 28 of Cycle 2 will be given orally under fasting conditions).
- [23] Return and dispensation of apatinib. Apatinib will be dispensed on Day 1 of Cycle 1 (dispensed to subjects in the drug expansion study from Day 22 of Cycle 1). From Day 1 of Cycle 2, the return and dispensation of apatinib will be performed on Day 1 of each cycle. The remaining drugs will be returned first to verify the dose actually taken before new study drugs are dispensed.
- [24] Imaging test: including CT or MRI of the chest, abdomen, and brain. The baseline tumor assessment during the screening period can be extended to up to 3 weeks before treatment. Qualified CT/MRI scan results obtained before signing the informed consent can be used for tumor assessment during the screening period. Bone scan should be performed upon clinically suspected bone metastasis. Absence of cerebral hemorrhage should be confirmed within 21 days before randomization for subjects with stable brain metastases.
- During the treatment period, imaging examinations should be performed under the same conditions as those at baseline (layer thickness of the scan, use of contrast agent, etc.), and the lesions found at baseline should be checked every 2 cycles in the first 6 cycles of the treatment (bone scan shall be performed in the case of suspected bone progression or for CR confirmation). After 6 cycles, imaging examinations can be performed every 3 weeks as appropriate and can be performed upon the discovery of suspected new lesions. Initial assessment of PR/CR must be confirmed after 4 weeks; initial assessment of PD must be confirmed after 4 to 6 weeks (except for significant changes in the subjects' symptoms or rapid tumor progression).
- The window period for imaging examination schedule is ± 7 days. Unscheduled imaging examinations can be performed when progressive disease is suspected (such as worsening of symptoms).
- [25] A tumor assessment is required at the end of treatment for subjects who discontinue study treatment for reasons other than radiographic PD, if not performed within 4 weeks prior to study completion. Also, treatment efficacy will be followed up once every 3 months after study completion, until documentation of confirmed PD or start of a new anti-tumor treatment.
- [26] Survival follow-up: After the study treatment is discontinued, the survival status and subsequent anti-tumor treatment can be collected through clinical or telephone follow-ups every 2 months until death.

- [27] PK blood sampling: In the stage of expanded PK study, PK blood sampling will be performed within 0.5 h before the administration of SHR-1210, and post-dose at 5 min (± 3 min), 2 h (± 10 min), 6 h (± 10 min), 24 h (± 0.5 h), 48 h (± 1 h), 168 h (± 1 h), 336 h (± 1 h), and 504 h (± 1 h) on D1, with 3 mL of blood collected at each time point. After the completion of PK blood sampling on D22, the administration of apatinib mesylate tablets will be started on the same day and continued at administration frequency of once a day. PK blood sampling will be performed within 0.5 h pre-dose on D28 and post-dose at 0.5 h (± 3 min), 1 h (± 5 min), 2 h (± 5 min), 3 h (± 5 min), 5 h (± 10 min), 8 h (± 10 min), 12 h (± 10 min), and 24 h (± 1 h), with 3 mL of blood collected at each time point.

On D1 of Cycle 2, PK blood sampling will be performed within 0.5 h before the administration of SHR-1210, and at 5 min (± 3 min), 2 h (± 10 min), 6 h (± 10 min), 24 h (± 0.5 h), 48 h (± 1 h), 168 h (± 1 h), and 336 h (± 1 h) after the administration of SHR-1210, with 3 mL of blood collected at each time point. On D28 of Cycle 2, PK blood sampling will be performed within 0.5 h before the administration of apatinib, and at 0.5 h (± 5 min), 1 h (± 5 min), 2 h (± 5 min), 3 h (± 5 min), 5 h (± 10 min), 8 h (± 10 min), 12 h (± 10 min), and 24 h (± 1 h) after the administration of apatinib, with 3 mL of blood collected at each time point.

- [28] A total of 14 mL of blood sample will be collected from each subject at baseline and divided into 1 tube of 10 mL and 1 tube of 4 mL. The collected blood samples will be transported to the central laboratory at room temperature according to the requirements specified in the central laboratory manual (no additional processing by the study center is required). Subjects with CR/PR during the study period must be subject to an additional biomarker blood sampling upon the onset of CR/PR and PD, respectively, with 10 mL in 1 tube, and the collection and transport requirements are the same as those in the baseline period; archived paraffin-embedded tumor tissue samples or fresh biopsy specimens will be collected. At least 10 slices are required, including 3-5 slices of 3-4 μm thickness for PD-L1 detection, and 5-8 slices of 5-8 μm thickness (paraffin blocks may be directly collected without mounting onto slides), otherwise fresh biopsy specimens are required for detection of biomarkers such as tumor mutation burden (TMB).

For cohort 4, the test results of tumor mutation burden (TMB) in the peripheral blood and/or tumor tissues will be verified before the subjects take the first dose of the study drug, so the TMB test for cohort 4 must be completed before the first dose. However, the delay in the screening period caused by TMB testing is allowed, but other tests (including imaging examinations) must be completed within 21 days prior to the first dose.

See the laboratory manual for biomarker blood sampling and tumor tissue sampling/sample collection and disposal.

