8.3 Collection and Follow-Up of AEs/SAEs

The collection of AEs/SAEs should start from the time when the subjects sign the informed consent form and end 90 days after the last dose of SHR-1210 or 30 days after the last dose of anti-angiogenic targeted therapy (whichever is longer). SAEs occurring after this period that are suspected to be related to the study drug should be collected. See [Table 8-1](#) below for specific requirements. Any AE/SAE should be followed-up until the event resolves, returns to the baseline level or \leq Grade 1, reaches a steady state, or is reasonably explained (e.g., lost to follow-up, death). The investigator should try to obtain the best outcome and clear causality with the study drug.

During each visit, the investigator should ask about the situation of AEs/SAEs that occur after the last visit and provide follow-up information in a timely manner based on the sponsor's query request.

Table 8-1. Collection period of AEs/SAEs

Classification	Collection/Recording Requirements
AEs Unrelated to the Study Drug	Up to 30 days after the last dose
Treatment-Related AEs ^a	Up to 90 days after the last dose of SHR-1210 or 30 days after the last dose of apatinib (whichever is longer)
SAEs Unrelated to the Study Drug ^a	
 Fatal SAEs: up to 90 days after the last dose of SHR-1210 or 30 days after the last dose of apatinib (whichever is longer) Non-fatal SAEs: up to 30 days after the last dose
Treatment-Related SAEs ^b	No time limit

^a Non-serious AEs

^b Including fatal and non-fatal SAEs.

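### The post-treatment AE window is stated inconsistently (30 days, 90 days, or split by causality), and no AE enquiry is assigned after the day-30 visit

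*Protocol*

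**What the plan says.** The protocol describes the end of AE collection in several places.

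- **Schedules of Activities (synopsis and section 7.4), AE row:** "From informed consent to 30 days after the last dose". The row carries footnote [14].
- **Footnote [14], sections 7.1 and 7.4:** a split by causality. Section 7.4 says "AEs unrelated to the study drugs will be recorded to 30 days after the last dose" and "Treatment-related AEs will be collected until 90 days after the last dose of SHR-1210", or 30 days after anti-angiogenic therapy if that is later. All three then refer to section 8.3 for detail.
- **Section 8.3, lead sentence:** collection of AEs/SAEs starts at consent and should "end 90 days after the last dose of SHR-1210 or 30 days after the last dose of anti-angiogenic targeted therapy (whichever is longer"). It sets no condition on relatedness.
- **Table 8-1, in the same section:** for unrelated AEs, "Up to 30 days after the last dose". Unrelated non-fatal SAEs have the same limit. For unrelated fatal events the table reads "Fatal SAEs: up to 90 days after the last dose of SHR-1210", or 30 days after apatinib if later. Related SAEs have no time limit.

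On follow-up contacts, section 7.4 lists AE review at a visit 30 days after treatment ends (± 3 days in the schedule). After that, "the survival status and subsequent anti-tumor treatment can be collected through clinical or telephone follow-ups every 2 months until death". Section 7.3 and footnote [25] add 3-monthly tumor assessment for subjects who stopped without radiographic progression. Neither later contact lists AE enquiry.

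**The concern.** The places that define the window disagree, and the section that the others defer to disagrees with itself. A site that follows the schedule row, the 8.3 lead sentence or Table 8-1 will collect different data.

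Separately, the protocol sets a 90-day window for SHR-1210-related AEs but assigns nobody to ask about them after day 30. Immune-related events are the ones most exposed. Sections 8.7 and 9.1 say that their diagnosis needs further serological, immunological and biopsy data and that infection and tumor must be excluded, so attribution may come late. Under Table 8-1, a non-fatal event with onset after day 30 is due for recording only once it is thought related.

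Incidence and severity of AEs and SAEs is the Stage I primary endpoint and a Stage II secondary endpoint. The analysis cannot restore an event that was never collected. SAP 4.2.1 puts no end date on treatment-emergent AEs, and SAP 5.4.3 counts missing causality as related, but both act only on events already in the database.

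**Working it through.** The plan states no figure on this point, so there is none to reproduce. The check compares the passages and then counts days.

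**Step 1. The rules side by side (days after last dose)**

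| Place | Related AE | Unrelated non-serious AE | Unrelated non-fatal SAE | Unrelated fatal SAE | Related SAE |
|---|---|---|---|---|---|
| AE row, both schedules | 30 | 30 | 30 | 30 | 30 |
| Footnote [14], 7.1, 7.4 | 90* | 30 | 30 | 30 | 90* |
| 8.3 lead sentence | 90* | 90* | 90* | 90* | 90*, later if suspected related |
| Table 8-1 | 90* | 30 | 30 | 90* | no limit |

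*90 days after SHR-1210 or 30 days after anti-angiogenic therapy (apatinib), whichever is longer. The first two rows speak of AEs in general. Their SAE entries are what results if SAEs are read as AEs.

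Footnote [14] corrects the AE row for related AEs. It does not settle the difference between the 8.3 lead sentence and Table 8-1 for unrelated AEs and unrelated non-fatal SAEs.

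**Step 2. Length of the window without an assigned enquiry**

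Let *m* be the number of days from the last SHR-1210 dose to the end of treatment, from which the day-30 visit is counted. The last visit with AE review then falls at day 30 + *m* after SHR-1210.

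Gap = max(0, 90 − (30 + *m*)) = max(0, 60 − *m*).

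- Both drugs stop together, *m* = 0: 90 − 30 = 60 days, and 60/90 = 67% of the window. With the ± 3 day visit window the gap is 57 to 63 days.
- Treatment ends when the next 2-weekly infusion would have been due, *m* = 14: 60 − 14 = 46 days, and 46/90 = 51%.
- Apatinib continues alone for 60 days or more, *m* ≥ 60: no gap, because on-treatment visits and then the day-30 visit cover the window.

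**Step 3. Contacts that already exist after day 30**

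If the 2-month interval runs from discontinuation and *m* = 0, survival contacts fall at about days 60 and 120. For subjects without radiographic progression, a 3-monthly tumor assessment falls at about day 90 ± 7, that is day 83 to 97. A question at the day-60 contact would reach back over days 31 to 60. The first contact after day 90 would close days 61 to 90.

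**The case against.** The strongest reply is that most of the protocol states one tiered rule. Footnote [14] sits on the very row that shows 30 days, and it agrees with 7.1, 7.4 and Table 8-1 on related AEs and unrelated non-serious AEs. The 8.3 lead sentence may be a loose summary, since it sends the reader to Table 8-1 for specifics. This stands in part. A reader of the row alone might infer that all AE collection ends at 30 days, and the documents do not support that. They do still leave the lead sentence and the table in conflict.

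A reader might also infer that an event in days 31 to 90 is recorded only if already judged related. That is too strong. Unrelated fatal SAEs run to day 90, related SAEs have no limit, and SAEs after the window need only be suspected to be related. Section 8.1.3 offers an indeterminable category, which section 13.4.4 counts as an adverse reaction. An event re-attributed within the window can be collected.

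Nor does the protocol forbid asking. Section 8.3 requires AE enquiry at each visit, section 5.3.2 asks for complete AE collection in withdrawn subjects, survival follow-up may be in person, and some subjects have an imaging visit near day 90. All of that stands. But nothing says that a survival telephone call is a visit, and no post-day-30 contact lists AEs among its items.

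Finally, splitting collection by causality is a legitimate choice. It limits the recording of events that belong to later anti-tumor therapy. This point therefore does not ask for it to be dropped.

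**Conclusion.** The inconsistency is plain in the text. So is the absence of an assigned AE enquiry for up to about 60 of the 90 days after SHR-1210. The 60-day figure assumes that both drugs stop together and that the day-30 visit is counted from the last dose. It falls day for day as treatment continues beyond the last SHR-1210 infusion.

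The consequence is a risk that late non-fatal immune-related events are under-recorded. It is not a demonstrated loss, and it does not apply to every subject. A reader might turn it into a count: assuming that 2% to 5% of the 174 Stage II subjects have a new event in days 31 to 90 gives 0.02 × 174 = 3.5 to 0.05 × 174 = 8.7 events. Those rates are not in the documents, and the count would include related and fatal events that Table 8-1 already requires sites to record. The number cannot be estimated from the documents.

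The Stage I tolerability decision rests on the first 28-day cycle and is not affected.

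**What to change.** 1. Reconcile the AE row in both schedules, both copies of footnote [14], sections 7.1 and 7.4, the 8.3 lead sentence and Table 8-1 to one stated rule. The AE row should no longer show 30 days for events that the protocol collects to 90. State which drug's last dose starts each period. Changing Table 8-1 alone would leave the footnote and sections 7.1 and 7.4 in conflict with it.
2. Add to section 7.4 and footnotes [25] and [26] that the planned survival and imaging contacts ask about AEs with onset up to the end of the 90-day window. The contacts needed are the first, at about day 60, and the next one after day 90.
3. State that suspected immune-related events are recorded when reported, with causality assessed afterwards.
4. The sponsor should decide, and write down, whether unrelated AEs are also collected to day 90. The SAP's treatment-emergent definition could then be given a matching end date.

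The cost is wording in the places listed, one extra question at contacts that already take place, and some additional AE entry. No new visit is needed.
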